9.4.4 ANALYSIS OF THE EXPLORATORY ENDPOINTS

- The first exploratory objective is to assess the feasibility of at-home self-administered SARS CoV-2 antigen tests. This will be measured via self-reported data on acceptability, practicality, integration, penetration, and demand of at-home self-administered antigen test. The proportion of respondents that find at-home self-administered antigen test acceptable will be analyzed for the entire study cohort and stratified by participant demographics (e.g., age, gender).

- The second exploratory objective is to assess participant mobility following SARS CoV-2 at-home test results over the study period. This will be evaluated using surrogate of mobility, including activity trackers.
- The third exploratory objective is to assess attitudes towards SARS CoV-2 vaccination over the study period. This will be measured via Health Belief Model Assessments using self-reported data on perceived susceptibility, severity, benefits, barriers, and cues to action related to SARS CoV-2 vaccination. The distribution of respondent's perception about SARS CoV-2 vaccination will be analyzed for the entire study cohort and stratified by participant demographics (e.g., age, gender).

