6. To assess the feasibility of at-home self-administered SARS CoV-2 antigen tests	Assessments: self-reported data on acceptability, practicality, integration, penetration, and demand of at-home self-administered antigen test	Proportion of respondents that find at-home self-administered antigen test acceptable for the entire study cohort and stratified by participant demographics (e.g., gender) of interest
7. To assess participant mobility following SARS CoV-2 at-home test results over the study period	Assessment: mobility patterns as captured by surrogates including activity trackers	Distribution of individual mobility data in response to positive vs. Negative SARS CoV-2 test results.
8. To assess attitudes towards SARS CoV-2 vaccination over the study period	Assessments: self-reported data on perceived susceptibility, severity, benefits, barriers, and cues to action related to SARS CoV-2 vaccination	Distribution of respondent's perception about SARS CoV-2 vaccination for the entire study cohort and stratified by participant demographics (e.g., gender) of interest

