8 STUDY ASSESSMENTS AND PROCEDURES

8.1 EFFICACY ASSESSMENTS

The questionnaires/surveys will assess patient-report outcomes related to social behaviors, healthcare utilization, knowledge of SARS CoV-2 prevention approaches, and the feasibility of at-home self-administered testing. Adherence to the at-home testing and questionnaire/survey schedule will also be assessed.

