9.3 POPULATIONS FOR ANALYSES

The following populations are also defined:

Population	Description
Evaluable Population- Per protocol (PP)	Per protocol population will be those that report adhering to the following: 
 1. Self-administer the at-home test three times a week for 4 weeks 2. Complete questionnaires/surveys during the 4 week testing period
Modified per-protocol	Will include any participant who performed at least one at-home test
Second modified per-protocol	Will include any participant who completed at least one survey

All analyses will be conducted in the PP. A subset of analyses will be repeated in the modified PP populations as applicable.

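### Feasibility (exploratory objective 6) rests on acceptability among Week 5 respondents, with a contradictory analysis set and no uptake or completion proportion over consented participants

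*Combined protocol and SAP*

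**What the plan says.** Section 3 lists feasibility as exploratory objective 6. Its assessments are "self-reported data on acceptability, practicality, integration, penetration, and demand of at-home self-administered antigen test", and its single endpoint is "Proportion of respondents that find at-home self-administered antigen test acceptable for the entire study cohort", with demographic strata. Section 9.4.4 repeats this: "The proportion of respondents that find at-home self-administered antigen test acceptable will be analyzed for the entire study cohort". The Schedule of Activities (Section 1.3) places the feasibility questionnaire at Week 5 only, the first time point after the four-week testing phase.

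Section 9.3 says "All analyses will be conducted in the PP". Membership of that set rests on the participant reporting two things: "Self-administer the at-home test three times a week for 4 weeks" and "Complete questionnaires/surveys during the 4 week testing period". Two wider sets are defined, one requiring at least one test and the other at least one survey. An unnamed subset of analyses is to be repeated in them. Section 4.4 says that partial testing and survey data will be analysed, however little there is.

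Section 8.1 adds "Adherence to the at-home testing and questionnaire/survey schedule will also be assessed". Section 9 gives this assessment no endpoint, denominator or analysis set. Sections 6.4 and 10.1.10 say that departures from the testing programme and protocol deviations are not tracked.

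**The concern.** Whether a regimen of frequent home tests is feasible depends largely on how many people start it and how many keep going. The only defined endpoint is an opinion, collected once at the end from those who reply. Neither starting nor persisting enters it.

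The unclear analysis set adds to this. Under Section 9.3, the opinion comes only from people who already did what is being judged for feasibility. Under Sections 3 and 9.4.4, people who gave up can contribute, but only if they answer at Week 5. Section 7.3 treats someone who fails testing and surveys and cannot be reached as withdrawn, so those who abandon testing may well be the ones missing.

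At stake is the feasibility conclusion: a high acceptability figure could be reported while many participants had stopped testing. Section 2.1 attributes earlier inconclusive home-testing results partly to poor promotion of uptake and consistent testing, and Section 4.2 lists non-compliance as a risk, so the question matters to this study.

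**Working it through.** **The plan's own figure.** No precision is stated for the feasibility endpoint. The general table in Section 9.2 gives a margin of 1.37% for a 50% proportion at N = 5,000. The simple formula gives 1.96 × √(0.5 × 0.5 / 5,000) = 1.386%. Multiplying by the finite-population factor √((300,000 − 5,000)/(300,000 − 1)), with the maximum sample of 300,000 from Section 5.5, gives 1.374%. All 12 table rows agree to two decimals on that basis. Precision is not the problem here.

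**Adherence in the PP set.** Membership requires 3 × 4 = 12 reported tests. Every member therefore has 12/12 = 100% reported testing adherence, whatever share of the cohort completes.

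**Acceptability in PP and in the whole cohort.** The documents give no completion or acceptability rates, so the following are assumptions. Let c be the share of consented participants who complete the regimen and surveys (PP), a1 acceptability among completers and a0 acceptability among the others. Assume also that completers who answer at Week 5 represent all completers; the PP definition does not itself require the Week 5 survey.

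- PP acceptability = a1
- Whole-cohort acceptability = c × a1 + (1 − c) × a0
- Difference = (1 − c) × (a1 − a0)

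With a1 = 90% and a0 = 50%:

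| c | PP acceptability | PP adherence | Whole-cohort acceptability | Completed and accept (c × a1) |
|---|---|---|---|---|
| 80% | 90% | 100% | 82% | 72% |
| 50% | 90% | 100% | 70% | 45% |
| 20% | 90% | 100% | 58% | 18% |
| 10% | 90% | 100% | 54% | 9% |

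The difference depends on the assumed gap. At c = 50% it is 0.5 × 40 = 20 points for a0 = 50%, 0.5 × 20 = 10 points for a0 = 70%, and zero for a0 = 90%. It changes sign if non-completers are the more accepting group.

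Without any assumption about a0, cohort acceptability lies between c × a1 and c × a1 + (1 − c). With a1 = 90% this is 72–92% at c = 80%, 45–95% at c = 50%, and 18–98% at c = 20%.

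**Entire cohort, Week 5 respondents only.** Suppose completers all respond and a fraction r of the others respond. The reported figure is (c × a1 + (1 − c) × r × a0) / (c + (1 − c) × r). With c = 50%, a1 = 90%, a0 = 50%:

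- r = 10%: 0.475/0.55 = 86%
- r = 30%: 0.525/0.65 = 81%
- r = 50%: 0.575/0.75 = 77%

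The whole-cohort value is 70% in each case. Moving to the entire cohort reduces the distortion but does not remove it.

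**What a completion proportion would show.** With 5,000 consented, completion over all of them would read 80% (±1.11), 50% (±1.39) or 20% (±1.11). The PP acceptability figure would read 90% each time, with its count falling to 4,000, 2,500 or 1,000 and its margin rising from 0.93 to 1.18 to 1.86 points.

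**The case against.** The strongest reply is that the PP set is not settled for this endpoint. Sections 3 and 9.4.4 name the entire cohort, Section 4.4 accepts partial data, and Section 9.3 itself provides wider sets. The at-least-one-survey set admits people who never tested and people who stopped. Section 8.1 does not place the adherence assessment in PP, and someone must review adherence across participants to form that set at all. Section 9.4.1 promises summaries of questionnaire data and testing results, with stratification by test or week number, and Section 9 defers further detail to a separate statistical analysis plan. A shrinking PP count would itself signal abandonment.

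Much of this stands. A reader might infer that feasibility will certainly be judged only among completers and that adherence will be reported as 100%. The documents do not support that; they contradict themselves on the set. A reader might also infer that the protocol treats non-compliance as its main threat, but Section 4.2 ranks slow enrollment first.

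Three things remain. The PP rule is stated without exception for this objective. Whether feasibility is among the analyses repeated in the wider sets is not said. And practicality, integration, penetration, demand and adherence are to be measured or assessed, but none has a defined endpoint. General summaries might allow a completion rate to be worked out, but none is planned as a feasibility result.

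**Conclusion.** The point holds in a limited form. Acceptability among Week 5 respondents is the only feasibility endpoint, its analysis set is contradictory, and no uptake or completion proportion over consented participants is specified. On the PP reading, completion does not enter the formula for the result; on the entire-cohort reading, those who stop and do not answer remain uncounted.

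The size of any bias in acceptability cannot be known from the documents. It is zero if completers and others accept equally, and 20 points (90% against 70%) under the illustrative case of 50% completion with 90% versus 50% acceptability. It would be too strong to say that the feasibility result is bound to be inflated or bound to pass: the plan sets no feasibility threshold, and acceptability among completers could itself vary with who stays. The consequence is confined to an exploratory conclusion in a mainly descriptive study; no primary or secondary result depends on it.

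**What to change.** 1. Reconcile Sections 3 and 9.4.4 with Section 9.3 by stating that the objective 6 analyses and the Section 8.1 adherence analyses are not run in the PP set.
2. Add to objective 6, with all consented participants as denominator: the proportion reporting at least one home test; the proportion reporting the complete schedule; and the distribution of the number of the 12 scheduled tests reported.
3. Report Week 5 acceptability for all who answer, beside the number of consented participants who did not, and split it by number of tests reported.

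The cost is protocol or SAP wording and a few tables. Sections 4.1 and 6.4 show that test results are already reported through the app or call center and that the app keeps a test history. There are limits. If reports are truthful, reported tests are a lower bound on tests taken. Consented participants are self-selected after receiving kits, so community-level uptake stays unobserved. The feasibility picture may also look less favourable.

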9.4.5 SAFETY ANALYSES

Not Applicable

9.4.6 BASELINE DESCRIPTIVE STATISTICS

Will be reported for demographic and medical history information.

9.4.7 PLANNED INTERIM ANALYSES

Not Applicable

9.4.8 SUB-GROUP ANALYSES

The majority of the primary, secondary, and exploratory endpoints analyses will also be stratified based on age, sex, race/ethnicity or other demographic characteristics.

9.4.9 TABULATION OF INDIVIDUAL PARTICIPANT DATA

Individual participant data and listings may be analyzed as needed during the study.

10 SUPPORTING DOCUMENTATION AND OPERATIONAL CONSIDERATIONS

10.1 REGULATORY, ETHICAL, AND STUDY OVERSIGHT CONSIDERATIONS

10.1.1 INFORMED CONSENT PROCESS

10.1.1.1 CONSENT/ASSENT AND OTHER INFORMATIONAL DOCUMENTS PROVIDED TO PARTICIPANTS

Consent forms describing in detail study procedures, and risks are given to the participants via the app (eConsent) or read to the participants through the phone (verbal consent). Informed consent is required prior to enrollment in this study. The following consent materials are submitted with this protocol: Adult ICF (above age 18), Age of Majority ICF (for those who turn 18 during the course of the study), and the Assent (below age 18).

10.1.1.2 CONSENT PROCEDURES AND DOCUMENTATION

Informed consent is a process that is initiated prior to the individual's agreeing to participate in the study and continues throughout the individual's study participation. Consent forms will be Institutional Review Board (IRB)-approved. Individuals participating via the app will be asked to read, review and electronically give their consent directly on the app. For individuals participating via the phone, the call center staff will explain the research study to the participant and answer any questions that may arise. A verbal explanation will be provided in terms suited to the participant's comprehension of the purposes, procedures, and potential risks of the study and of their rights as research participants. Participants will have the opportunity to ask questions prior to giving their verbal consent. Participants must be informed that participation is voluntary and that they may withdraw from the study at any time, without prejudice. The informed consent process will be conducted and documented, including the date consented, before the participant undergoes any study-specific procedures.

10.1.2 STUDY DISCONTINUATION AND CLOSURE

This study may be temporarily suspended or prematurely terminated if there is sufficient reasonable cause. Written notification, documenting the reason for study suspension or termination, will be provided by the suspending or terminating party to study participants, investigator, funding agency, the sponsor and regulatory authorities. If the study is prematurely terminated or suspended, PI will promptly inform study participants, the IRB, and sponsor and will provide the reason(s) for the termination or suspension. Study participants will be contacted, as applicable, and be informed of changes to study schedule.

Circumstances that may warrant termination or suspension include, but are not limited to:

- Determination of unexpected, significant, or unacceptable risk to participants
- Demonstration of efficacy that would warrant stopping
- Insufficient compliance to protocol requirements

- Data that are not sufficiently complete and/or evaluable
- Determination that the primary endpoint has been met
- Determination of futility

Study may resume once concerns about safety, protocol compliance, and data quality are addressed, and satisfy the sponsor and IRB.

10.1.3 CONFIDENTIALITY AND PRIVACY

Participant confidentiality and privacy is strictly held in trust by the participating investigators, their staff, and the sponsor and their interventions. No information concerning the study or the individual participant data will be released to any unauthorized third party without prior written approval of the sponsor.

The study participant's contact information will be securely saved for internal use during the study. At the end of the study, all records will continue to be saved securely for as long a period as dictated by the reviewing IRB, Institutional policies, or sponsor requirements.

Study participant research data collected via the app or the call center, which is for purposes of statistical analysis and scientific reporting, will be securely stored. This will not include the participant's contact or identifying information. Data transmitted to CareEvolution will be de-identified when extracted by the study team. Information collected by the CareEvolution app will be securely stored on CareEvolution servers in the United States, or on servers owned by third party service providers that CareEvolution contracts with to securely store information in the United States. The study data entry and study management systems will be secured and password protected. At the end of the study, all study data from the app will be de-identified and archived.

10.1.4 FUTURE USE OF STORED SPECIMENS AND DATA

Data generated from this study will be analyzed in this study. In addition, the NIH Data Sharing Policy applies to this study, and de-identified data from this study will be made available to other researchers.

No data will be shared with the test manufacturer and the data generated in this study will not be used to support any regulatory claims.

All participants in the sub-study will have the option to consent to re-contacting for future research. An option to opt-out of re-contacting will also be provided in the consent.

10.1.6 SAFETY OVERSIGHT

Since there are no medications or interventions being prescribed as part of the study, and due to the minimal risk of the survey data only the study will not have a Data and Safety Monitoring Board (DSMB). Instead, the DCRI PI will serve as the medical monitor.

10.1.7 CLINICAL MONITORING

As a direct-to-family study, the study will take place directly in a participant's home and there will be no formal monitoring of the study. Study personnel will still ensure that the rights and well-being of study participants are protected, that the reported study data are accurate, complete, and verifiable, and that the conduct of the study is in compliance with the currently approved protocol, International Conference on Harmonisation Good Clinical Practice (ICH GCP), and with applicable regulatory requirement(s).

10.1.8 QUALITY ASSURANCE AND QUALITY CONTROL

The DCRI will perform internal quality management of study conduct, data collection, documentation and completion.

Quality control (QC) procedures will be implemented beginning with the data entry system and data QC checks that will be run on the database. The study team will be responsible for monitoring data collected via the mobile application to ensure that the reported study data are accurate, and complete, reported in compliance with the protocol, International Conference on Harmonisation Good Clinical Practice (ICH GCP), and applicable regulatory requirements (e.g., Good Laboratory Practices (GLP), Good Manufacturing Practices (GMP)).

The study team will provide access to all study related source data/documents, and reports for the purpose of monitoring and auditing by the sponsor, and inspection by local and regulatory authorities.

10.1.9 DATA HANDLING AND RECORD KEEPING

10.1.9.1 DATA COLLECTION AND MANAGEMENT RESPONSIBILITIES

Using PhenX and RADx-Up CDE measures, the questionnaires/surveys will collect data on demographic characteristics, medical history and health status, SARS-CoV-2 testing and symptoms, social interactions, knowledge of prevention strategies, and infection risk, and attitudes towards vaccines. All data capture will be electronic for participants who choose to participate using the MyDataHelps app. The app platform will be the technology that underpins data collection and management. The mobile application functions as a communication platform between the participants, investigators, and the study team. It supports daily reminders, seamless data collection, surveys/questionnaires, and data exchange between participants and the study team. In addition to its function as a communication platform, it is also a source documentation platform that is used to record, document, and store all information collected by the study team. All source data entered into the application has an audit trail, which documents who completes data entry and when, with all data legibly recorded. Study team members entering source data into the application do so in real time as they are collecting the data. For those participating via the phone calls, the data provided by the participant will be documented into the app by the call center member.

10.1.9.2 STUDY RECORDS RETENTION

Study documents should be retained for a minimum of 2 years after the last approval of a marketing application in an International Conference on Harmonization (ICH) region and until there are no pending or contemplated marketing applications in an ICH region or until at least 2 years have elapsed since the formal discontinuation of clinical development of the study intervention. These documents should be retained for a longer period, however, if required by local regulations. No records will be destroyed without the written consent of the sponsor, if applicable. It is the responsibility of the sponsor to inform the investigator when these documents no longer need to be retained.

10.1.10 PROTOCOL DEVIATIONS

Protocol deviations will not be collected or tracked for this observational study.

10.1.11 PUBLICATION AND DATA SHARING POLICY

This study will be conducted in accordance with the following publication and data sharing policies and regulations:

National Institutes of Health (NIH) Public Access Policy, which ensures that the public has access to the published results of NIH funded research. It requires scientists to submit final peer-reviewed journal manuscripts that arise from NIH funds to the digital archive [PubMed Central](#) upon acceptance for publication.

This study will comply with the NIH Data Sharing Policy and Policy on the Dissemination of NIH-Funded Clinical Trial Information and the Clinical Trials Registration and Results Information Submission rule. As such, this study will be registered at ClinicalTrials.gov, and results information from this study will be submitted to ClinicalTrials.gov. In addition, every attempt will be made to publish results in peer-reviewed journals. Data from this study may be requested from other researchers 10 years after the completion of the primary endpoint by contacting [name] or [name].

10.1.12 CONFLICT OF INTEREST POLICY

The independence of this study from any actual or perceived influence, such as by the pharmaceutical industry, is critical. Therefore, any actual conflict of interest of persons who have a role in the design, conduct, analysis, publication, or any aspect of this study will be disclosed and managed. Furthermore, persons who have a perceived conflict of interest will be required to have such conflicts managed in a way that is appropriate to their participation in the design and conduct of this study. The study leadership in conjunction with the NIH Institute has established policies and procedures for all study group members to disclose all conflicts of interest and will establish a mechanism for the management of all reported dualities of interest.

10.2 ABBREVIATIONS

AE	Adverse Event
CFR	Code of Federal Regulations
CRF	Case Report Form
DCC	Data Coordinating Center
eCRF	Electronic Case Report Forms
FDA	Food and Drug Administration
GCP	Good Clinical Practice
GLP	Good Laboratory Practices
GMP	Good Manufacturing Practices
HIPAA	Health Insurance Portability and Accountability Act
ICH	International Conference on Harmonisation
ICMJE	International Committee of Medical Journal Editors
IRB	Institutional Review Board
MedDRA	Medical Dictionary for Regulatory Activities
SOE	Nares swab
NIH	National Institutes of Health
NIH IC	NIH Institute or Center
PI	Principal Investigator
QA	Quality Assurance
QC	Quality Control
RADX-UP	Rapid Acceleration for Diagnostics in Underserved Populations
SAE	Serious Adverse Event
SOA	Schedule of Activities
SOC	System Organ Class
SOP	Standard Operating Procedure
US	United States

